#### Monitoring Of non-hematological $\geq$ grade 3 toxicities

With the concern of treatment related toxicity, the non-hematological toxicity ( $\geq$ grade 3) will also be closely monitored during the study. Since the 6 patients treated at MTD in phase I will be included for efficacy evaluation in phase II, the toxicity monitoring in phase II start either with the 7th patient or with the 1st patient treated at the MTD.

Denote the probability of toxicity by  $P_E$ . We assume  $P_E \sim \text{beta} (0.6,1.4)$ . Our stopping rule is given by the following probability statement:  $\text{Pr}(P_E > 0.3 \mid \text{data}) > 0.9$ . That is, we will stop the trial if, at any time during the study, we determine that there is more than 90% chance that the toxicity is more than 30%. The study will be stopped early if (The number of non-hematological toxicities being grade 3 or higher)/ (The number of patients evaluated)  $\geq 4/6, 5/8, 6/10, 7/13, 8/15, 9/18, 10/21$ . The operating characteristics are summarized in table 3.

Table 3: Operating characteristics for monitoring of non-hematological  $\geq$ grade 3 toxicities

| True Toxicity Rate | Early Stopping Probability | Median Sample size (interquartile) |
|--------------------|----------------------------|------------------------------------|
| 0.2                | 0.05                       | 22 (22,22)                         |

|     |      |             |
|-----|------|-------------|
| 0.3 | 0.22 | 22 (22, 22) |
| 0.4 | 0.54 | 19 (7, 22)  |
| 0.5 | 0.82 | 7 (6, 17)   |

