### **Dose Escalation Procedures**

The dose of treatment agent will be escalated in successive cohorts of patients. The starting dose is at dose 0 as shown in table 1. Enroll 3 patients at the dose level and proceed to the next higher dose level with a cohort of 3 patients until at least 1 patient experiences a dose-limiting toxicity (DLT).

DLT is defined as a clinically significant adverse event or abnormal laboratory value assessed as unrelated to disease progression, intercurrent illness, or concomitant medications and meeting the NCI common terminology criteria that are CTCAE Grade 3 or 4.

An adverse event must be clinically significant to define DLT e.g. alopecia, study drug-related fever, electrolyte abnormalities (including K, Na, Cl, HCO3, Mg, Ca) that are < Grade 3 will not define the DLT. Drug-related Grade 3-4 nausea and vomiting not controlled with adequate therapy will be considered DLTs.

If only 1 of 3 patients experiences a DLT at a given dose level, enter 3 additional patients at the current dose level. If only 1 of 6 patients experiences a DLT at a given dose level, proceed to the next higher dose level with a cohort of 3 patients. If at least 2 of 3 or 2 of up to 6 patients experience a DLT at a

given dose level, then the MTD has been exceeded (stopping dose). Once the MTD has been exceeded, treat another 3 patients at the previous dose level if there were only 3 patients treated at that dose level. The MTD is defined as the highest dose level in which 6 patients were treated with at most 1 experiencing a DLT during the 1st cycle.

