## Phase II

Phase II part is a single arm study using the dosage level recommended from phase I. The patients treated at the MTD in phase I will be included in phase II part, and the sample size for phase II can be up to 22. The trial will be continuously monitored for efficacy and toxicity (non-hematological  $\geq$ grade 3). The method of Thall, Simon, and Estey will be used to perform interim efficacy and safety monitoring (15).

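### Table 3 describes 22 unselected patients, but the first six at the MTD are there only because at most one had a DLT, so it overstates how often the phase II toxicity rule stops once phase II begins

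*Protocol*

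**What the plan says.** Dose Escalation Procedures (Protocol, repeated in the SAP): "The MTD is defined as the highest dose level in which 6 patients were treated with at most 1 experiencing a DLT", judged over the first cycle. A DLT there is a clinically significant grade 3 or 4 event not attributed to progression, intercurrent illness or concomitant medication.

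Phase II (both documents): "The patients treated at the MTD in phase I will be included in phase II part". The stated maximum for this part is 22 patients.

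The Protocol section on monitoring non-hematological toxicity of grade 3 or higher repeats the carry-over with a number: "Since the 6 patients treated at MTD in phase I will be included for efficacy evaluation in phase II". It puts a Beta(0.6, 1.4) prior on the toxicity rate. The trial stops if "we determine that there is more than 90% chance that the toxicity is more than 30" per cent, with boundaries "4/6, 5/8, 6/10, 7/13, 8/15, 9/18, 10/21". On where the count begins it says that "the toxicity monitoring in phase II start either with the 7th patient or with the 1st patient treated at the MTD". It gives one table of operating characteristics, Table 3, and does not say whether that table allows for the MTD condition. The available SAP text ends before this section.

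**The concern.** The six patients who open the phase II count are not a random sample at that dose. A dose with two or more DLTs in six is never the MTD, so phase II begins only after a low-toxicity start. Where the monitored toxicities are also DLTs, the early boundaries cannot be reached and the six favourable results dilute every later look.

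The rule matters most when a too-toxic dose has passed phase I by chance. Someone relying on Table 3 would believe that a 40% toxicity rate then triggers a stop about half the time.

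**Working it through.** **Inputs (Protocol).** Prior Beta(0.6, 1.4); stop if Pr(rate > 0.30 | data) > 0.90; maximum 22 patients; six carried in; MTD requires at most 1 DLT in 6.

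**1. Boundaries.** After t toxicities in n patients the posterior is Beta(0.6 + t, 1.4 + n − t). For 4/6 this is Beta(4.6, 3.4), with Pr(rate > 0.30) = 0.945; for 3/6 it is 0.80. The printed fractions are change points, so the boundary b(n) is 4 at n = 6–7, 5 at 8–9, 6 at 10–12, 7 at 13–14, 8 at 15–17, 9 at 18–20 and 10 at 21.

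**2. Reproducing Table 3.** Let q(n, t) be the probability of being unstopped after n patients with t toxicities. Then q(n, t) = (1 − p)·q(n−1, t) + p·q(n−1, t−1), and the mass with t ≥ b(n) moves to the stopping probability. With 22 independent patients and looks after patients 6 to 21:

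| True rate | Table 3 | Recomputed | Recomputed median (quartiles) |
|---|---|---|---|
| 0.2 | 0.05 | 0.050 | 22 (22, 22) |
| 0.3 | 0.22 | 0.228 | 22 (22, 22) |
| 0.4 | 0.54 | 0.539 | 19 (7, 22) |
| 0.5 | 0.82 | 0.824 | 7 (6, 17) |

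All medians and quartiles match the printed ones. Table 3 therefore treats the first six as unselected.

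**3. Counting from the 1st MTD patient, every monitored toxicity a DLT.** The recursion restarts at n = 6 with only 0 or 1 toxicity. The probability of that condition is S = (1 − p)^6 + 6p(1 − p)^5. At p = 0.4, S = 0.0467 + 0.1866 = 0.233; at p = 0.5, S = 7/64 = 0.109. The most toxicities possible by patient n is 1 + (n − 6), that is 3/8, 5/10 and 6/11. The first reachable boundary is 6/11, so Table 3's sample sizes of 6 and 7 could not occur in this case.

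**4. Partial overlap.** Let f be the share of monitored toxicities that are DLTs, with no DLTs from other events. The weight on k toxicities in the first six is then proportional to C(6, k)·p^k·(1 − p)^(6−k)·Pr(Bin(k, f) ≤ 1).

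**5. Fresh count from the 7th patient.** The recursion of step 2 is run on 16 new patients, with looks at 6 to 15 of the new count.

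Stopping before the last patient, same convention throughout:

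| Case | 20% | 30% | 40% | 50% |
|---|---|---|---|---|
| Table 3 | 0.05 | 0.22 | 0.54 | 0.82 |
| From 1st MTD patient, f = 1 | 0.003 | 0.034 | 0.155 | 0.400 |
| f = 0.75 | 0.013 | 0.090 | 0.305 | 0.618 |
| f = 0.50 | 0.028 | 0.153 | 0.425 | 0.737 |
| f = 0.25 | 0.043 | 0.204 | 0.506 | 0.801 |
| Fresh 16 from the 7th | 0.046 | 0.191 | 0.442 | 0.712 |

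Counting a crossing at the last patient raises these slightly: at 40% and 50%, f = 1 becomes 0.175 and 0.445, and the fresh count becomes 0.459 and 0.736.

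**6. Phase I and II combined, counting from the 1st MTD patient.** The chance that the dose is not declared the MTD, or is stopped later with probability r, is 1 − S(1 − r).
- f = 1: at 40%, 1 − 0.233 × 0.845 = 0.80; at 50%, 1 − 0.109 × 0.600 = 0.93.
- f = 0.25: at 40%, 1 − 0.886 × 0.494 = 0.56; at 50%, 1 − 0.833 × 0.199 = 0.83.

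**The case against.** Table 3 is correctly computed for the rule as printed, and the protocol does not present it as conditional on phase I. The stronger reading, that the phase II rule simply stops far less often than stated, needs two premises that the documents do not set.

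First, the six must be in the toxicity count, and the protocol leaves the start open. With a fresh count from the 7th patient selection has no effect; the remaining shortfall comes from having 16 patients rather than 22.

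Second, most monitored toxicities must be DLTs. A DLT is filtered for clinical significance and attribution, and the MTD is judged on the first cycle. The phase II count carries no such filter, while treatment runs for months and systemic chemotherapy and irradiation are allowed. Full overlap is therefore the extreme case, and at 25% overlap the figures are close to Table 3.

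A reader might also infer that patients are less protected across the whole trial than Table 3 suggests. That does not follow. Phase I removes most toxic doses itself, and the combined figures in step 6 are no worse than Table 3 at 40% and 50%.

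These limits stand, and they set the size of the point. They do not rescue the table. Under the start from the 1st MTD patient it ignores selection; under a fresh count from the 7th it describes a different number of patients.

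**Conclusion.** The point holds in a limited form. Table 3 overstates phase II stopping, given that phase II has begun, in every case computed. The size depends on an open choice and an unstated overlap. At 40% toxicity the printed 0.54 compares with values from 0.155 (full overlap) to 0.506 (25% overlap) when counting from the 1st MTD patient, and with 0.442 on a fresh count. At 50% the printed 0.82 compares with 0.400 to 0.801, and with 0.712.

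The calculations assume independent patients, a constant toxicity rate, DLTs arising only among monitored toxicities, and a look after every patient from the sixth in the count. The overlap values are illustrative. The claim concerns the phase II rule, not the protection given by phases I and II together.

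**What to change.** State whether toxicity counting starts with the 1st MTD patient or the 7th, whether the six remain in the count, and how a DLT relates to the monitored toxicity (attribution, clinical significance, time window).

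Then replace Table 3. If the six are counted, give figures conditional on at most 1 DLT among them, over a stated range of overlap. If counting starts afresh with the 7th patient, give figures for 16 new patients. Use one convention for the last look. Beside the table, print the combined phase I and II probability that the dose is not declared the MTD or is later stopped, and the earliest patient at which the rule can act.

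The cost is a rerun of the simulation and a replaced table. The stated phase II stopping probabilities become less favourable; the fix itself requires no change to treatment or sample size.

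### The phase II toxicity rule as worded is already met at 2 of 2 and 3 of 4 patients, but the printed boundaries and Table 3 assume no look before about the 6th counted patient

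*Protocol*

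**What the plan says.** All of this is in the Protocol. The available SAP text ends within the efficacy rule, before toxicity monitoring.

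- **Probability statement** (toxicity monitoring section): prior Beta(0.6, 1.4); stop when Pr(P_E > 0.3 | data) > 0.9. In words, "we will stop the trial if, at any time during the study, we determine that there is more than 90% chance" that the rate is above 30%. The Phase II section adds "The trial will be continuously monitored for efficacy and toxicity".
- **Boundary list** (same section): stop at or above "4/6, 5/8, 6/10, 7/13, 8/15, 9/18, 10/21".
- **Operating characteristics**: "The operating characteristics are summarized in table 3". At true rates 0.2, 0.3, 0.4 and 0.5, Table 3 gives stopping probabilities 0.05, 0.22, 0.54 and 0.82, and median (interquartile) sample sizes 22 (22,22), 22 (22,22), 19 (7,22) and 7 (6,17).
- **Start of counting**: "the toxicity monitoring in phase II start either with the 7th patient or with the 1st patient treated at the MTD".
- **Cap** (Phase II section): MTD patients from phase I are carried in, and "the sample size for phase II can be up to 22".
- **Rule for the first patients at a dose** (Dose Escalation Procedures): 3+3, in which two DLTs among three, or among up to six, mean that the MTD is exceeded.

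**The concern.** The section states one stopping rule twice, as a posterior probability and as a list of counts. The two should give the same decision at every look, and before the 6th counted patient they do not. At 2 of 2 or 3 of 4 the probability statement says stop, while the list has no entry. The plan sets no minimum number of patients before the first look and leaves the start of counting open between two options.

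This is the phase II safety stopping rule. A team and a monitoring body could reach different decisions on the same data, each with support in the text. Table 3 would also be read as describing the probability statement above it, when it describes a rule with a later first look.

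**Working it through.** **Inputs** (Protocol): prior Beta(0.6, 1.4), threshold 0.3, cutoff 0.9, maximum 22 patients.

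**Formula.** After x toxicities in n counted patients the posterior is Beta(0.6 + x, 1.4 + n − x). Stop if its upper tail beyond 0.3 exceeds 0.9.

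**Step 1: reproduce the printed list.** From n = 6 the smallest stopping counts are 4 (n = 6–7), 5 (8–9), 6 (10–12), 7 (13–14), 8 (15–17), 9 (18–20) and 10 (21–22). That is exactly the printed list with each count carried forward, so the prior and cutoff have been read as intended.

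**Step 2: the same formula before n = 6.**

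| x/n | Posterior | Pr(P_E > 0.3) | Stop? |
|---|---|---|---|
| 1/1 | Beta(1.6, 1.4) | 0.789 | no |
| 2/2 | Beta(2.6, 1.4) | 0.928 | yes |
| 2/3 | Beta(2.6, 2.4) | 0.838 | no |
| 3/3 | Beta(3.6, 1.4) | 0.976 | yes |
| 3/4 | Beta(3.6, 2.4) | 0.935 | yes |
| 3/5 | Beta(3.6, 3.4) | 0.875 | no |
| 4/5 | Beta(4.6, 2.4) | 0.975 | yes |

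Only 2/2 and 3/4 act. Once 2/2 stops the trial, 3/3 cannot occur; once 2/2 and 3/4 stop it, 4/5 cannot occur.

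**Step 3: reproduce Table 3.** Exact recursion over 22 patients with a look after each; a crossing at patient 22 is not counted as early.

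| True rate | Table 3 | First look at n = 6 | Wording applied from patient 1 | Difference of last two |
|---|---|---|---|---|
| 0.2 | 0.05; 22 (22,22) | 0.050; 22 (22,22) | 0.084; 22 (22,22) | 0.0836 − 0.0501 = 0.0335 |
| 0.3 | 0.22; 22 (22,22) | 0.228; 22 (22,22) | 0.274; 22 (17,22) | 0.2735 − 0.2277 = 0.0458 |
| 0.4 | 0.54; 19 (7,22) | 0.539; 19 (7,22) | 0.573; 16 (6,22) | 0.5734 − 0.5385 = 0.0349 |
| 0.5 | 0.82; 7 (6,17) | 0.824; 7 (6,17) | 0.839; 7 (2,16) | 0.8390 − 0.8240 = 0.0150 |

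With a first look at n = 6, every median and quartile matches Table 3, and each stopping probability agrees to within 0.01. A first look at n = 5 fits equally well, since 4/5 always becomes at least 4/6 one patient later. A first look at n = 4 does not fit (0.062, 0.246, 0.553, 0.831; median 17 at rate 0.4). A first look at n = 7 changes one entry: the lower quartile at rate 0.5 becomes 7.

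**Step 4: chance of meeting an early boundary.** The paths are 2/2, with probability p², or one event in the first two patients followed by two more, with probability 2p³(1 − p).

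- p = 0.2: 0.0400 + 0.0128 = 0.053
- p = 0.3: 0.0900 + 0.0378 = 0.128
- p = 0.4: 0.1600 + 0.0768 = 0.237
- p = 0.5: 0.2500 + 0.1250 = 0.375

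Most of these trials would stop under the printed list too, except at the lowest rate. The share is 1 − (difference in step 3)/(chance here): about 37%, 64%, 85% and 96%. The fall in expected sample size is 0.7 to 1.9 patients (21.33 − 20.59 at rate 0.2; 11.40 − 9.55 at rate 0.5).

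**The case against.** **Nothing printed is miscalculated.** A reader might infer that Table 3 is wrong. It is not: it reproduces for the printed list. The conflict is between that pair and the unqualified timing in the probability statement. This stands in full.

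**The count may be cumulative, with a first look at the 7th patient.** On that reading the first six MTD patients are counted, the list needs nothing before n = 6, and there is no conflict. The MTD definition requires six treated patients, which fits a list beginning at six. A reader might instead infer that the count restarts at the 7th patient, leaving patients 7 to 11 without a boundary. The Protocol's own figures contradict that. The cap of 22 includes the MTD patients, so a restarted count could reach only 22 − 6 = 16; the 9/18 and 10/21 boundaries could never be used, and Table 3 could not show 22. The cumulative reading is therefore the better one for that option. However, the text does not state it, and it offers the 1st MTD patient as an alternative start.

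**The 3+3 rule already protects these patients.** A reader might infer that enrolment would carry on after 2 of 2 or 3 of 4 severe toxicities. That does not follow when the events are first-cycle DLTs, because two in up to six already exceed the MTD. The objection stands for those events, but the two rules count different things. A DLT must be clinically significant and judged unrelated to progression, intercurrent illness or concomitant medication, and the MTD rests on the first cycle. The phase II rule is written for any non-hematological event of grade 3 or higher, although its opening sentence refers to treatment-related toxicity. Systemic chemotherapy and irradiation are permitted alongside, and dosing continues for 4 + 8 = 12 weeks after CSF clearance. Countable events that are not DLTs, or that come after the first cycle, are therefore possible.

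**Conclusion.** The point holds as an internal inconsistency. The probability statement and the boundary list disagree at 2/2 and 3/4; the list and Table 3 are consistent with each other and assume no look before about the 6th counted patient.

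The conflict has practical effect only if counting starts with the 1st MTD patient, and then for grade 3 or higher non-hematological events that are not DLTs or that fall after the first cycle. It does not arise if the first look is at the 7th patient with the first six counted.

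On the exact calculation, early stopping changes by about 1.5 to 4.6 percentage points. The timing of stops moves more: at a true rate of 50% the lower quartile falls from 6 patients to 2, and at 40% the median falls from 19 to 16. These figures assume independent patients with a constant toxicity rate, immediate outcome assessment and no selection of the first MTD patients by the 3+3 rule. Because of that last assumption, they and the 5% to 38% chance of meeting an early boundary are upper bounds. If every counted event were a first-cycle DLT, the chance at a dose declared the MTD would be zero.

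This is a clarification worth making before the rule is used. It does not invalidate the monitoring design.

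**What to change.** Reconcile four items in the Protocol's toxicity monitoring section, and in any matching SAP text: the start of counting, the probability statement, the boundary list and Table 3. Either route makes them agree.

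1. **Keep the timing as worded.** Add 2/2 and 3/4 to the list, state that counting starts with the 1st MTD patient, and rerun Table 3. The stated stopping probability at 20% toxicity then rises from 0.05 to about 0.08.
2. **Keep the list and Table 3.** Replace the unqualified timing with the first look that Table 3 assumes (about the 6th counted patient), state that earlier MTD patients are counted cumulatively, and say that the 3+3 rule in Dose Escalation Procedures governs before then. No rerun is needed.

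The choice belongs to the sponsor and investigators. The cost is a sentence or two, plus one rerun of Table 3 under the first route.

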### **Analysis method**

Data analysis will be performed using SAS or S-plus, as appropriate. All patients who received at least 1 dose of the agent will be included in the intent-to-treat analysis for efficacy. Demographic and disease characteristics of the patients at registration will be summarized using descriptive statistics such as mean, standard deviation (SD), median and range. Overall response rates will be presented with 95% confidence intervals. The association between response and patient and disease characteristics will be examined by two-sample t-test or Chi-square test.

The data from all patients who received the therapy during the study will be included for safety analysis. Safety data will include laboratory, physical exam, and adverse event reports on study patients. These descriptive summaries will be provided for all patients for each safety parameter by intrathecal rituximab dose #, grade, and relationship to treatment.

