### **Statistical Considerations**

The primary outcome of the study will be response rate. Time to recurrence of CNS leukemia and overall survival will be secondary outcomes. Time to recurrence and survival will be considered from the date of CNS relapse diagnosis.

There is no well-defined metric to measure response to treatment in patients with peripheral nerve involvement only. Clinical and radiologic response will be recorded and it is expected that few to no patients with only peripheral nerve involvement will actually be involved and therefore the statistical analysis will not be affected.

A maximum of 25 patients will be enrolled in this phase I/II study, with about 12 patients/year.

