## **Efficacy**

The primary endpoint is the response defined as the CNS is without evidence of blast cells after four lumbar punctures with rituximab. The historical data suggested the response rate by chemotherapy (methotrexate and/or cytarabine) is about 10%. The targeted improved overall response rate is 25%, The trial will be continuously monitored. The study will be stopped early if the data suggest that:

$$\Pr(\pi > 0.1 | \text{data}) < 0.05$$

Here  $\pi$  is the response rate. That is, if at any time during the study we determine that there is a less than 5% chance that the response rate is greater than 10%, we will terminate the study. The response

rate is assumed to follow a non-informative prior of Beta (0.2, 1.8). The study will be stopped early if (The number of responders)/ (The number of patients evaluated)  $\leq 0/9$ .

Table 2: Operating characteristics for monitoring of overall response rate

| True Response Rate | Early Stopping Probability | Median Sample size (interquartile) |
|--------------------|----------------------------|------------------------------------|
| 0.05               | 0.63                       | 9 (9, 22)                          |
| 0.1                | 0.40                       | 22 (9,22)                          |
| 0.15               | 0.23                       | 22 (22,22)                         |
| 0.2                | 0.14                       | 22 (22,22)                         |
| 0.25               | 0.08                       | 22 (22,22)                         |

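### Associations with response are to be tested by t-test or Chi-square with about 2 to 6 responders expected, so the Chi-square p-values are unreliable in either direction; small-sample tests should be named

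*Protocol*

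**What the plan says.** Under Analysis method, the protocol states: "The association between response and patient and disease characteristics" "will be examined by two-sample t-test or Chi-square test". It gives no exact or rank-based fallback, significance level, list of characteristics or exploratory label. It does not say whether the Chi-square test is continuity-corrected. The SAP text available ends within the Efficacy section, before this material, so the point rests on the protocol.

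The likely number of responders follows from other sections:

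- Efficacy gives the historical rate: "the response rate by chemotherapy (methotrexate and/or cytarabine) is about 10" per cent.
- Efficacy also gives the target: "The targeted improved overall response rate is 25" per cent.
- Phase II states that "the sample size for phase II can be up to 22".
- Statistical Considerations sets the overall limit: "A maximum of 25 patients will be enrolled in this phase I/II study".
- Analysis method defines the efficacy population: "All patients who received at least 1 dose of the agent will be included in the intent-to-treat analysis for efficacy". The analysed number could therefore be as high as 25.

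**The concern.** Both named tests rely on approximations that need a reasonable number of patients in each response group. On the plan's own assumptions the responder group will be a handful. The Chi-square reference distribution is then a poor match for the few values the statistic can take. The t-test would compare a few patients with 16 to 20 others, with little averaging to offset skewness.

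This is the only stated test of who responds. One responder falling in a very small subgroup could be reported as a significant predictor, and a real difference could go unremarked. Small subgroups are plausible because eligibility covers any CD20-positive lymphoid malignancy, children from age 3, and peripheral nerve infiltration.

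**Working it through.** **Inputs.** N = 22 (Phase II) or 25 (Statistical Considerations); response rates 0.10 and 0.25 (Efficacy); prior: "rate is assumed to follow a non-informative prior of Beta (0.2, 1.8"). Assumed, because the plan is silent: two-sided 0.05, the subgroup sizes, and the shape of any continuous variable.

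**1. The plan's own figures.** With no responders in n patients the posterior is Beta(0.2, 1.8 + n). Pr(rate > 0.1) is 0.0531 at n = 8 and 0.0453 at n = 9, so the 0/9 boundary is reproduced. Early stopping is then (1 − p)^9 = 0.630, 0.387, 0.232, 0.134 and 0.075 for p = 0.05, 0.10, 0.15, 0.20 and 0.25. Table 2 gives 0.63, 0.40, 0.23, 0.14 and 0.08. The plan states no operating characteristics for the association tests.

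**2. Expected responders.** 22 × 0.10 = 2.2 and 22 × 0.25 = 5.5. With 25 patients: 2.5 and 6.25.

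**3. Expected cell counts.** With r responders and m patients in the smaller subgroup, the smallest expected count is r × m/N when r is at most N/2. The most favourable split of 22 is 11/11, and 9 × 11/22 = 4.5, still below 5. The chance of 9 or fewer responders among 22 is 0.97 at a 25% rate and above 0.999 at 10%.

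**4. One table.** Two responders, a two-patient subgroup, one responder in it: cells 1, 1 / 1, 19.

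- Uncorrected Chi-square: 22 × (1×19 − 1×1)² / (2×20×2×20) = 22 × 324/1600 = 4.455, p = 0.035.
- Continuity-corrected: 22 × (18 − 11)² / 1600 = 0.674, p = 0.41.
- Exact: 1 − C(20,2)/C(22,2) = 1 − 190/231 = 0.177.

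**5. All tables in range.** For N = 22, 2 to 6 responders and subgroups of 1 to 11 (5 × 11 = 55 sets of margins), the hypergeometric distribution gives the chance of p < 0.05 when there is no association.

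| Test | Conditional size over the 55 tables |
|---|---|
| Uncorrected Chi-square | 0 to 18%; mean 4.7%, median 3.8%; above 5% in 20, above 10% in 6 |
| Continuity-corrected | at most 3.8% |
| Fisher's exact | at most 4.6% |

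High values for the uncorrected test include 17.7% (2 responders, subgroup of 2), 12.1% (2 with 8, and 6 with 7) and 11.6% (5 with 9). It is 0 for 2 responders with subgroups of 9 to 11. Averaged over the number of responders (N = 22 and 25; rates 0.10 and 0.25; subgroups of 3, 5, 7 and 11), its size is 1.2% to 7.6%.

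**6. Continuous characteristics.** Simulation, N = 22, lognormal variable with log-SD 1, responders shifted by 1.5 log-SD. Power:

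| Responders | Lower values: t / exact rank-sum | Higher values: t / exact rank-sum |
|---|---|---|
| 2 | 0.5% / 37% | 62% / 38% |
| 4 | 11% / 65% | 77% / 66% |
| 6 | 32% / 82% | 81% / 82% |

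Repeat runs differ by about a point, so for lower values the ranges are roughly 1–33% against 36–83%. A t-test on the log scale has 49%, 74% and 85% in this setting, in either direction.

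**The case against.** A reader might infer that the planned Chi-square test generally produces false associations. The documents do not support that. The 12–18% figures are the peaks: the mean and median sizes are below 5%, and 35 of the 55 tables are at or below it. The protocol also leaves the continuity correction open, and with it the test is conservative throughout. What stands is narrower: for the margins actually observed, the p-value may be far too small or unable to reach significance, and the plan does not settle which version applies.

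A reader might also infer that the t-test misses real differences on skewed variables in general. It does not. When responders have the higher values of a right-skewed variable, it matches or beats the rank-sum test in the cases above. The loss is confined to the other direction. Moreover, the plan lists no characteristics and does not rule out a log scale. CSF protein and leukocyte count appear in the Diagnosis section as diagnostic findings, not as planned covariates. The t-test part is therefore secondary.

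The count of 2 to 6 responders depends on the planning rates. The background sections report clearance in all 7 patients of one series and a high response rate in another. If response were very common, non-responders would be the small group and the problem would return; at intermediate rates it eases.

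Finally, little depends on this analysis. It is secondary and unpowered, with no decision attached, and exact tests cannot supply missing information. With 2 responders and an 11/11 split no result can reach 0.05. All of this stands, and it limits the importance of the point without removing it.

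**Conclusion.** The concern holds in limited form. On the plan's own rates the Chi-square approximation is almost never in its usual range, and no alternative is named. The uncorrected test has a conditional size between 0 and about 18% (median about 4%), so its error runs in both directions; a corrected version would be conservative. The t-test can miss a difference when responders have the lower values of a right-skewed variable, and only then.

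The Chi-square figures assume a two-sided 0.05 and the subgroup sizes examined. The t-test figures also assume a lognormal variable and a 1.5 log-SD shift. The primary response rate with its confidence interval, the efficacy and toxicity stopping rules, and dose selection are untouched. This is a minor point, worth making because the correction is so cheap.

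**What to change.** In Analysis method, replace the named tests with: *Fisher's exact test for categorical characteristics and the exact Wilcoxon rank-sum test for continuous characteristics (or a t-test on a pre-specified log scale for skewed variables)*. Add that these analyses are exploratory. Listing the characteristics in advance would help.

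The cost is one sentence, with no new data and no change to sample size or design. The downside is that Fisher's test is conservative here: its size is 0 for 2 responders with subgroups of 6 to 11, so fewer binary characteristics will reach 0.05. Exact tests correct the error rate; they do not cure the low power.
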